10.6 Therapeutic Equivalence Analysis

Therapeutic equivalence of the Test product to the Reference product based on the primary endpoint will be evaluated in the PP population after the end of treatment on Day 8 + 1. If the 90% confidence interval (calculated using Yates’ continuity correction) for the absolute difference between the proportion of patients considered as “Responders” (at least a 25% reduction from baseline in the sum of % basal/parabasal + % intermediate cells on vaginal cytology AND vaginal pH < 5.0 with a change from baseline vaginal pH of at least 0.5) in the Test and Reference groups is contained within the range [-20%, +20%] then bioequivalence of the Test product to the Reference product will be considered to have been demonstrated for the primary endpoint.

Therapeutic equivalence of the Test product to the Reference product based on the secondary endpoint will be evaluated in the PP population after the end of treatment on Day 8 + 1. Secondary analysis will compare the proportion of patients considered to be a “Treatment Success” for their most bothersome symptom. A “Treatment Success” is defined as a score of 0 or 1 at Day 8 for the symptom identified at baseline as the most bothersome. If the 90% confidence interval (calculated using Yates’ continuity correction) for the absolute difference between the proportion of patients considered as “Treatment Success” in the Test and Reference groups is contained within the range [-20%, +20%] then bioequivalence of the Test product to the Reference product will be considered to have been demonstrated for the secondary endpoint.

To declare therapeutic equivalence of the Test product to the Reference product, bioequivalence must be demonstrated for only the primary endpoint. Bioequivalence testing of the secondary endpoint will be conducted for supportive information.

CONFIDENTIAL PROTOCOL

A Randomized, Double-Blind, Placebo-Controlled, Parallel Design, Multiple-Site Study to Evaluate the Therapeutic Equivalence of Estradiol Vaginal Cream USP, 0.01% (Teva Pharmaceuticals, USA) to Estrace® Estradiol Vaginal Cream, USP, 0.01% (Warner Chilcott) in the Treatment of Atrophic Vaginitis

10.7 Superiority to Placebo Analysis

Superiority of the Test and Reference products against the Placebo for primary and secondary endpoints will be tested at the 5% significance level ($p < 0.05$; using two-sided, continuity-corrected Z-test) in the mITT population using last observation carried forward. The superiority of Test and Reference treatments over the Placebo will be evaluated identically in separate Z-Test analyses.

10.8 Safety Analysis

All study patients who use at least one application of the study drugs will be included in the safety analysis. Adverse events will be classified using standard MedDRA terminology Version 17.0 or higher and summarized by treatment group. Summary tables comparing the type, incidence, severity and Investigator's opinion to drug relationship relation will be prepared by treatment group. Signs and symptoms of atrophic vaginitis will not be considered adverse events, unless in the Investigator's opinion, they have increased in frequency and/or severity to such an extent that the Investigator/patient considers that it is in the patient's best interest to be dropped from continued participation in the study and given alternative therapy for their condition. If sufficient data exist, adverse event frequencies will be compared between treatments using Fisher's exact test or a similar test. Concomitant medication use during the study will be tabulated by patient. Adverse events reported during the study will be tabulated in a summary table listing the type, incidence, severity and Investigator's opinion to drug relationship.

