Efficacy Endpoints	
Primary Efficacy Endpoint
 
The primary efficacy endpoint is the proportion of patients in the Per Protocol (PP) population that are identified as "Responders" at the end of the treatment period evaluated on Day 8 + 1.
 
A responder is defined as a patient with at least a 25% reduction from baseline in the sum of % basal/parabasal + % intermediate cells on vaginal cytology AND vaginal pH < 5.0 with a change from baseline vaginal pH of at least 0.5.
 
Secondary Efficacy Endpoint
 
The secondary efficacy endpoint is the proportion of patients in the PP population that are identified as "Treatment Success" at the end of the treatment period evaluated on Day 8 + 1.
 
A "Treatment Success" is defined as a score of 0 or 1 at Day 8 + 1 for the symptom identified at baseline as the most bothersome. This evaluation is to

CONFIDENTIAL PROTOCOL

A Randomized, Double-Blind, Placebo-Controlled, Parallel Design, Multiple-Site Study to Evaluate the Therapeutic Equivalence of Estradiol Vaginal Cream USP, 0.01% (Teva Pharmaceuticals, USA) to Estrace® Estradiol Vaginal Cream, USP, 0.01% (Warner Chilcott) in the Treatment of Atrophic Vaginitis

	
be based on patient self-assessed symptoms of vulvar and vaginal atrophy on a scale of 0 to 3 where 0 = none and 3 = severe. Refer to Appendix B for rating scales.

Safety Parameters	
Adverse events will be classified using standard MedDRA terminology and summarized by treatment group. Summary tables comparing the type, incidence, severity and Investigator's opinion of relationship to the study drug will be prepared by treatment group. Signs and symptoms of atrophic vaginitis will not be considered adverse events, unless in the Investigator's opinion, they have increased in frequency and/or severity to such an extent that the Investigator/patient considers that it is in the patient's best interest to be dropped from continued participation in the study and given alternative therapy for their atrophic vaginitis.
 
If sufficient data exist, adverse event frequencies will be compared between treatments using Fisher's exact test or a similar test. Concomitant medication use during the randomized treatment period will be tabulated by patient. Adverse events reported during the study will be tabulated in a summary table listing the type, incidence, severity and Investigator's opinion to drug relationship.

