9.6.6 Rating of Symptoms

At Visits 1, 2 and 3 the blinded clinical staff or Investigator will question the patient regarding the severity of their atrophic vaginitis symptoms (see Appendix B for rating scales). The following symptoms will be evaluated:

- Vaginal Dryness
- Vaginal/Vulvar irritation/itching
- Dysuria
- Vaginal Pain associated with Sexual Activity
- Vaginal Bleeding

The severity of each symptom will be recorded on the source documents. The patients will be asked to identify which symptom is considered to be the most bothersome symptom at each visit.

CONFIDENTIAL PROTOCOL

A Randomized, Double-Blind, Placebo-Controlled, Parallel Design, Multiple-Site Study to Evaluate the Therapeutic Equivalence of Estradiol Vaginal Cream USP, 0.01% (Teva Pharmaceuticals, USA) to Estrace[®] Estradiol Vaginal Cream, USP, 0.01% (Warner Chilcott) in the Treatment of Atrophic Vaginitis

The worsening in severity of the signs and symptoms need not be additionally included as an adverse event, unless the patient requires additional treatment or the condition is an AE in the opinion of the Investigator.

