9.7 Adverse Events

The patients will be monitored throughout the study for any adverse experiences. AEs will be collected through both solicited and unsolicited means and subsequently coded in tabular form using the MedDRA Version 17.0 or higher adverse event dictionary. The patients will be encouraged to report signs, symptoms, and any changes in health to the clinic staff. Severity of each AE will be determined by the clinic staff based on observation and questioning of the patient. The Investigator will judge the relationship of the event to the study treatments.

Definitions

An adverse event is any untoward medical occurrence in a clinical investigational patient administered a pharmaceutical product, regardless of whether it has a causal relationship with this treatment. In this study, any adverse event occurring after the patient has signed the informed consent form should be recorded and reported as an adverse event.

An adverse event can, therefore, be any unfavorable and unintended physical sign, symptom, or laboratory parameter that develops or worsens in severity during the course of the study, or significant worsening of the disease under study or of any concurrent disease, whether or not considered related to the study drug. A new condition or the worsening of a pre-existing condition will be considered an adverse event. Stable chronic conditions (such as arthritis) that are present before study entry and do not worsen during the study will not be considered adverse events.

Abnormal results of diagnostic procedures, including laboratory findings, are considered to be AEs if the abnormality:

- results in study withdrawal
- is associated with a serious adverse event (SAE)
- is associated with clinical signs or symptoms
- is considered by the physician to be of clinical significance

CONFIDENTIAL PROTOCOL

A Randomized, Double-Blind, Placebo-Controlled, Parallel Design, Multiple-Site Study to Evaluate the Therapeutic Equivalence of Estradiol Vaginal Cream USP, 0.01% (Teva Pharmaceuticals, USA) to Estrace® Estradiol Vaginal Cream, USP, 0.01% (Warner Chilcott) in the Treatment of Atrophic Vaginitis

This includes events not seen at baseline, or worsened if present at baseline.

Recording and Reporting Adverse Events

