Treatment Group	Patient Randomization Number	Date of First Dose	Date of Last Dose	Total Number of Dose Administered	Dosing Compliance (%)
Test	XX-XXXX	yyyy-mm-dd	yyyy-mm-dd	XX	XXX.X

Reference Placebo

Test: Estradiol Vaginal Cream, USP, 0.01% (Teva Pharmaceuticals, USA)

Reference: Estrace® Cream (estradiol vaginal cream, USP, 0.01%; Warner Chilcott)

Placebo: Placebo cream (Teva Pharmaceuticals, USA)

Path: L:\Studies_Sas_Codes\Clinical Trial\71436001\PDF\xxx

L16.2.5.3 Listing of Study Compliance

Treatment Group	Patient Randomi- zation Number	Dose on the day of Visit 3?	Use any restricted medication for the treatment of atrophic vaginitis?	Use any restricted medication other than for the treatment of atrophic vaginitis?	Administer < 6 or >8 of the intended doses?	Miss >1 dose of study medication?	Develop any concurrent vaginal infection or illness?	Require additional treatment?
Test	XX-XXXX	No	No	No	No	No	No	No

Test: Estradiol Vaginal Cream, USP, 0.01% (Teva Pharmaceuticals, USA)

Reference: Estrace® Cream (estradiol vaginal cream, USP, 0.01%; Warner Chilcott)

Placebo: Placebo cream (Teva Pharmaceuticals, USA)

Path: L:\Studies_Sas_Codes\Clinical Trial\71436001\PDF\xxx

L16.2.6.1 Listing of Vaginal Cytology Results (Test: Estradiol Vaginal Cream, USP, 0.01%)

		BaselineVisit 3											
Patient Rando- mization	Basal/ Parabasal	Inter- mediate	Basal/ Parabasal +Inter-	Super- ficial		Basal/ Parabasal	Inter- mediate	Basal/ Parabasal +Inter-	Super- ficial		Cytology Changes From	pH Changes From	Responder
Number	%	%	mediate%	Cells%	pН	%	%	mediate%	Cells%	pН	Baseline	Baseline	Yes/No
xx-xxxx	69	31	100	100	7.0	12	43	55	100	4.5	45	2.5	Yes

Programming note: table will continue for reference and placebo group

Path: L:\Studies_Sas_Codes\Clinical Trial\71436001\PDF\xxx

Page 1 of N

L16.2.6.2 Listing of Signs and Symptoms Ratings

	Patient		Baseline Most				
Treatment	Randomization	Most Bothersome	Most Bothersome	Bothersome	Success		
Group	Number	Symptom at Baseline	Score at Baseline	Symptom Score at V3	(Yes/No)		
Test	XX-XXXX	Vaginal Dryness	3	0	Yes		

Reference

Placebo

Test: Estradiol Vaginal Cream, USP, 0.01% (Teva Pharmaceuticals, USA)

Reference: Estrace® Cream (estradiol vaginal cream, USP, 0.01%; Warner Chilcott)

Placebo: Placebo cream (Teva Pharmaceuticals, USA)

Path: L:\Studies Sas Codes\Clinical Trial\71436001\PDF\xxx

L16.2.7 Listing of Adverse Events by Treatment Group

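### Protocol 10.8 and the Synopsis set a narrower adverse event rule for worsening vaginal symptoms than 9.6.6 and 9.7, and no planned SAP output shows Visit 3 scores beyond the most bothersome symptom

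*Protocol*

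**What the plan says.** **AE rules in the protocol**

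- Section 10.8: "Signs and symptoms of atrophic vaginitis will not be considered adverse events", except where the Investigator finds an increase so marked that the Investigator or patient considers it "in the patient's best interest to be dropped from continued participation in the study and given alternative therapy for their condition". The Synopsis (Safety Parameters) repeats this, with the threshold that the patient be "dropped from continued participation in the study and given alternative therapy for their atrophic vaginitis".
- Section 9.6.6: "The worsening in severity of the signs and symptoms need not be additionally included as an adverse event". The two exceptions are a need for further treatment and a judgement by the Investigator that it is an AE. Withdrawal is not required.
- Section 9.7: the AE definition takes in any unfavourable symptom that appears or becomes more severe during the study, "or significant worsening of the disease under study or of any concurrent disease". The recording rules in the same section require every AE to go on the source document and CRF whatever its severity.

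**SAP**

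- Section 8.3.1 codes and tabulates all AEs reported. It neither repeats the 10.8 exclusion nor gives a rule of its own for worsened study symptoms.
- Section 8.2 has all five symptoms scored at Visits 1, 2 and 3: dryness, irritation/itching, dysuria, pain with sexual activity and bleeding.
- All five appear in the shells at baseline only (T16.1.9.4 to T16.1.9.6 and L16.2.4.2). At Visit 3 the shells carry only the symptom most bothersome at baseline: as success or failure in T16.1.9.8, and as a score in "L16.2.6.2 Listing of Signs and Symptoms Ratings".

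**The concern.** Irritation, itching and dysuria are symptoms of the disease and also plausible local reactions to a vaginal cream. If a site treats them as disease symptoms and follows 10.8, a patient can feel clearly worse on the cream, finish her 7 days and leave no AE record. Section 9.6.6 says worsening need not be *additionally* reported, which presumes that the symptom scores carry the information. The planned outputs do not show most of those scores.

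Objective 3 is to compare the safety of Test, Reference and Placebo. A difference between the two active creams in local tolerability is the kind of finding that comparison should be able to show. Sites acting in good faith under different sections would also record the same event differently.

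**Working it through.** The plan gives no figure on this point, so the check sets the rules and outputs side by side.

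**Step 1. Possible changes on one symptom.** The irritation/itching scale runs from 0 to 3 (Protocol Appendix B; SAP Appendix A). There are 4 × 4 = 16 pairs of pre-dose and Visit 3 scores. Those with a higher Visit 3 score number 4 × 3 / 2 = 6: 0→1, 0→2, 0→3, 1→2, 1→3 and 2→3. Dysuria uses the same range, so the count is the same.

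**Step 2. Apply each rule to one patient.** Her most bothersome symptom at baseline is dryness. Her irritation gets worse, and she completes treatment with no need for withdrawal or extra treatment.

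| Rule | Condition for an AE | Worsenings that are AEs |
|---|---|---|
| 10.8 and Synopsis | Worsening that warrants dropping the patient and alternative therapy | 0 of 6 |
| 9.6.6 | Additional treatment needed, or Investigator's opinion | 0 to 6 of 6 |
| 9.7 | Symptom appears or worsens | 6 of 6 |

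One could argue that for the study disease 9.7 requires *significant* worsening, so some one-step changes might drop out. A change from 0 to 3 would still be an AE under 9.7 and still not under 10.8 if it is treated as a disease symptom.

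**Step 3. Where the 10.8 threshold can be met.** The only scheduled visit after dosing starts is Visit 3, which is also the end of the study. A patient who reaches it has almost no participation left to be dropped from.

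**Step 4. Do the symptom outputs show the change?** Five symptoms are scored at Visit 3 and one per patient is displayed, leaving 5 − 1 = 4 in no planned table or listing. For the patient in Step 2, the number of planned outputs showing her Visit 3 irritation score is 0.

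If irritation were her most bothersome symptom with a baseline score of 2, then 2→2 and 2→3 would both count as not a success in T16.1.9.8. Only L16.2.6.2 would separate them.

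**Result.** Under 10.8, even a change from none to severe can be absent from both the AE tables and the symptom outputs.

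**The case against.** The strongest reply is that 10.8 and the Synopsis are the outliers, and that they may do little in practice. Site-facing recording instructions are in 9.6.6 and 9.7. Section 9.6.6 is permissive: its Investigator-opinion clause admits anything 9.7 would count. SAP 8.3.1 takes all reported AEs and does not carry the 10.8 exclusion forward, so an event recorded under 9.6.6 or 9.7 reaches the tables. This stands, and it fixes where the conflict lies: 10.8 and the Synopsis against 9.6.6 and 9.7, not three mutually incompatible rules.

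There are also safety nets:

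- Adverse findings at the Visit 3 examination are to be reported as AEs, and examination results are listed.
- Patients record AEs in the diary and are asked an open-ended AE question at each contact.
- L16.2.5.3 lists any need for additional treatment and any concurrent vaginal infection or illness.

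These reduce the gap but do not close it. A completer with patient-rated irritation and a normal examination can pass through all of them if the site regards her symptom as disease and follows 10.8.

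It can further be said that itching in a patient who had none is a new reaction, outside 10.8. That reading is available, but 10.8 does not state it and the same symptom is on the disease list, so the site has to decide.

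Finally, the SAP says its shells may not cover every aspect of the study, and datasets are to be provided. So the scores are not lost; they are in no *planned* table or listing.

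**Conclusion.** The inconsistency is real and bears on Objective 3. Local reactions in patients who complete treatment **can** be missing from the safety comparison. This rests on two conditions: that at least some sites apply 10.8 or the Synopsis when recording, and that the final outputs follow the shells. The primary equivalence decision does not depend on it.

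The size can be given only by case: 0 of 6 possible worsenings on a four-level symptom are AEs under 10.8 for a completer, against 6 of 6 under the plain wording of 9.7, with 4 of 5 Visit 3 scores per patient undisplayed. The documents give no rate of local reaction and no baseline symptom distribution, so no count of affected patients follows.

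Three stronger conclusions are tempting but unsupported:

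- A reader might infer that these reactions will be counted as zero in every arm. That needs every site to follow 10.8 and disregard 9.6.6 and 9.7.
- A reader might infer that vaginal bleeding in general is hidden. The rating scale covers only bleeding during or after sexual activity; other bleeding falls under 9.7.
- A reader might infer that most patients have room to worsen because entry needs only one moderate to severe symptom. A minimum entry rule does not show how the other scores are distributed.

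**What to change.** 1. **Protocol.** Reconcile 10.8 and the Synopsis with 9.6.6 and 9.7 into one AE recording rule for signs and symptoms of atrophic vaginitis, and refer to it from SAP 8.3.1.
2. **SAP table.** Add a Safety-population table, by arm and symptom, of the number and percent of patients whose Visit 3 score is higher than their pre-dose score.
   - State which visit is baseline. SAP 8.1.2 takes baseline signs and symptoms from the initial visit, whereas Visit 2 gives the last score before dosing.
   - Use patients with both scores as the denominator.
   - For the two sexual-activity items, include only patients with a rating at both visits.
3. **SAP listing.** Show all five Visit 3 scores in L16.2.6.2.

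The table is useful whichever AE rule is chosen, and also where sites have already recorded under different rules. It needs no new assessments. The cost is wording in both documents, one table and extra columns in a listing. The downside is that more AEs may be recorded in all arms.

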11.0 REGULATORY OBLIGATIONS

11.1 Institutional Review Board

The study protocol, informed consent form, Investigator's Brochure, or package insert (as applicable), and any specific advertising will be submitted to, and approved by, an Institutional Review Board (IRB) before the start of the study. A form must be signed by the chairman or designee of the IRB noting the approvals. This notification of the board's approval along with a description by profession and gender of the board's composition will be provided to the Sponsor.

11.2 Study Documentation

This study will be conducted in compliance with the protocol, Good Clinical Practices (GCPs) and all applicable regulations, including the Federal Food, Drug and Cosmetics Act, US applicable Code of Federal Regulations (title 21), parts 50, 56, 312, 320 and any IRB requirements relative to clinical studies and the Declaration of Helsinki, June 1964, as modified by the 59th World Medical Association General Assembly, October 2008.

The Investigator will permit trial-related monitoring, audits, IRB review and regulatory inspections providing direct access to source data/documents.

CONFIDENTIAL PROTOCOL

A Randomized, Double-Blind, Placebo-Controlled, Parallel Design, Multiple-Site Study to Evaluate the Therapeutic Equivalence of Estradiol Vaginal Cream USP, 0.01% (Teva Pharmaceuticals, USA) to Estrace® Estradiol Vaginal Cream, USP, 0.01% (Warner Chilcott) in the Treatment of Atrophic Vaginitis

11.2.1 Protocol

The Investigator indicated on FDA Form 1572 will act as the Principal Investigator at each study site. Protocols will be noted as approved by placement of the [REDACTED] Representative's signature on the cover page. The Sponsor of the study will also approve the protocol by having a study-responsible individual sign the protocol cover page.

11.2.2 Informed Consent

An Informed Consent Form (ICF) that includes all of the relevant elements currently required by FDA and local State regulations will be provided to each prospective study patient before enrollment into the study. The type and method of study, tests to be administered, any potential or possible hazards, and the patient's right to withdraw from the study at any time will be explained to the patients by the Investigator or designee. Once the Investigator or designee is assured that an individual candidate understands the implications of participating in this study, the patient will be asked to give consent by signing and dating in the appropriate areas of the ICF. The Investigator or designee will also sign and date the form, along with a staff member who will sign the ICF as a witness to verify that the patient has indeed received information. For illiterate patients, verbal consent should be obtained in the presence of and be countersigned by a literate witness. If any other language is required, translation will be performed by a certified translator. A copy of the ICF will be provided to the patient.

11.2.3 Protocol and Informed Consent Changes

Revisions to the original protocol will be documented in amendments, incorporated as a preface to the new version and approved by the IRB. Any revision that substantially alters the study design or increases potential risk to the patient requires the patient's consent to continue in the study. Revisions to the original ICF will also be approved by the IRB. The approvals will be processed in accordance with the established IRB procedures. Copies of all protocol and ICF amendments/revisions, along with letters noting IRB approval, will be submitted to the Sponsor.

